5.1. Screening data and recruitment

The target population of this study includes naïve adult patients of both genders with chronic myeloid leukemia in chronic phase.

Written informed consent must be obtained before performing any study specific medical procedures. The screening visit will take place at study days -28 to zero.

The screening RT-qPCR blood sample will be analyzed by a Sponsor designated central laboratory. In case the BCR-ABL1 status cannot be determined on this sample (e.g., due to technical or logistical issues) another blood sample for RT-qPCR is to be collected immediately and submitted to the central laboratory for determination of the BCR-ABL1 status.

Laboratory baseline assessments (including hematology and chemistry), physical examination including performance status, height, weight, ECG and vital signs must be performed within 28 days prior to Cycle 1/study Day 1, before the first IMP dose. As long as a patient that has signed the IC fulfil all inclusion criteria and none of the exclusion criteria, he/she could be included in this study.

5.2. Eligibility criteria

Inclusion Criteria -Patients eligible for inclusion in this study have fulfil the following criteria:

1. Male or female patient \geq 18 years of age.
2. Evidence of a personally signed and dated informed consent document indicating that the patient (or a legal representative) has been informed of all pertinent aspects of the study.
3. Patients who are willing and able to comply with scheduled visits, treatment plan, laboratory tests, and other study procedures
4. Newly Patient with Philadelphia chromosome positive chronic phase CML and BCR-ABL1 transcript detected at diagnosis.
5. ECOG Performance Status of 0, 1, or 2.
6. Adequate hepatic, renal and pancreatic function defined as:
 - a. Total bilirubin within normal range or Direct bilirubin \leq 1.5 x ULN,
 - b. Aspartate aminotransferase (AST)/Alanine aminotransferase (ALT) \leq 2.5 x upper limit of normal (ULN) or \leq 5 x ULN if attributable to liver involvement of leukemia,
7. Have a negative pregnancy test documented prior to enrolment (for females of childbearing potential). A woman is considered of childbearing potential, i.e., fertile, following menarche and until becoming post-menopausal unless permanently sterile. Permanent sterilization methods include hysterectomy, bilateral salpingectomy and bilateral oophorectomy (CTFG, 21/09/2020). These women must have a negative serum or urine pregnancy test before initiation of study treatment and must also use highly effective methods of contraception while enrolled in the study. The use of highly effective contraception should continue for at least 14 days after the last dose of study treatment. Acceptable forms of highly effective contraception methods include (CTFG, 21/09/2020):
 - a. Total abstinence [when this is in line with the preferred and usual lifestyle of the patient. Periodic abstinence (e.g., calendar, ovulation, symptothermal, post-ovulation methods) and withdrawal are not acceptable methods of contraception]
 - b. Male/female sterilization. These defined as:

- i. Female sterilization (have had surgical bilateral oophorectomy with or without hysterectomy) or tubal ligation at least six weeks before taking study treatment. In case of oophorectomy alone, only when the reproductive status of the woman has been confirmed and documented by follow-up hormone level assessment.
- ii. Male sterilization (at least 6 months prior to screening). For female patients on the study, study participation assumes the vasectomised male partner is the sole partner for that patient.

c. Contraceptive methods:

- i. Combined (estrogen and progestogen containing) hormonal contraception associated with inhibition of ovulation: oral, intravaginal, or transdermal.
- ii. Progestogen-only hormonal contraception associated with inhibition of ovulation: oral, injectable, or implantable.
- iii. Placement of an intrauterine device (IUD) or intrauterine system (IUS).

Women are considered post-menopausal and not of child bearing potential if they have had 12 months of natural (spontaneous) amenorrhea with an appropriate clinical profile (e.g., age appropriate, history of vasomotor symptoms) or have had surgical bilateral oophorectomy with or without hysterectomy or tubal ligation at least six weeks prior to enrolling. In the case of oophorectomy alone, only when the reproductive status of the woman has been confirmed by follow-up hormone level assessment is she considered not of child bearing potential.

If a study patient gets pregnant or is suspected of being pregnant during the study or within 30 days as part of safety evaluations after the final dose of bosutinib, the study Doctor needs to be informed immediately and any ongoing study treatment with bosutinib has to be stopped immediately.

Exclusion Criteria - Patients eligible for this study must not fulfil the following criteria:

1. Pregnant or lactating women,
2. Participation in another clinical trial with any investigational drug within 30 days prior to study enrolment,
3. Any prior medical treatment for CML including tyrosine kinase inhibitors (TKIs) with the exception of hydroxyurea,
4. Period of time since CML diagnosis longer than 6 months,
5. Hypersensitivity to the active substances or to any of the excipients of the bosutinib and/or atezolizumab formulations,
6. Major surgery or radiotherapy within 14 days of enrolment,
7. Known clinically significant liver disease, including active viral, alcoholic, or other hepatitis, cirrhosis, and inherited liver disease,
8. Concomitant use of or need for medications known to prolong the QT interval,
9. Concomitant use with strong CYP3A inhibitors (ketoconazole, itraconazole, clarithromycin), moderate CYP3A inhibitors (erythromycin, fluconazole, diltiazem), or strong CYP3A inducers (rifampin, carbamazepine, phenytoin),
10. History of clinically significant or uncontrolled cardiac disease, including:
 - a. Stage II to IV congestive heart failure (CHF) as determined by the New York Heart Association (NYHA) classification system for heart failure,
 - b. Myocardial infarction within the previous 6 months,
 - c. Symptomatic cardiac arrhythmia requiring treatment,
 - d. Diagnosed or suspected congenital or acquired prolonged QT history or prolonged QTc. (QTcF should not exceed 500 msec),
11. Grade III or IV fluid retention,
12. Uncontrolled hypomagnesemia or uncorrected symptomatic hypokalemia, due to potential effects on the QT interval,
13. Uncontrolled or symptomatic hypercalcemia,

14. Recent or ongoing clinically significant gastrointestinal (GI) disorder e.g. Crohn's Disease, Ulcerative Colitis or prior total or partial gastrectomy,
15. Autoimmune or infectious active disease that require treatment,
16. CML patient not in chronic phase at diagnosis,
17. Patients with known atypical transcript. An atypical transcript is defined by the presence of any transcript in the absence of the major transcripts b3a2 (e14a2) and b2a2 (e13a2) or p210 protein,
18. Patients with known resistant mutation(s) (T315I, E255K/V, Y253H, F359C/V). It is not necessary to perform mutation tests on the patient to be included in the study if they were not previously performed,
19. Individuals with an active malignancy,
20. Known seropositivity to human immunodeficiency virus (HIV), current acute or chronic hepatitis B (hepatitis B surface-antigen positive) and/or hepatitis C,
21. Any other disease, metabolic dysfunction, physical examination finding, or clinical laboratory finding that contraindicates the use of an investigational drug,
22. Patients with severe renal impairment.

5.3. Withdrawal/follow-up

Patients may suspend their participation in the study whenever they wish, based on his/her own judgement and opinion, without giving any explanation, although the investigator may investigate the reasons of a voluntary dropout.

The investigator may also decide to withdraw a patient from the trial if he/she does not comply with the protocol, due to AEs or treatment inefficacy or toxicity.

Patients who do not comply with at least 70% of the scheduled doses of bosutinib or that, in 4 or more times, the administration of atezolizumab is cancelled, will be withdrawn from the study.

6. Statistical Principles

6.1. General features

Principal features of this analysis have been specified in the protocol according to ICH E3 ("Structure and content of clinical study reports") and ICH E9 ("Statistical Principles for Clinical Trials" and addendum Draft R1).

This is a phase Ib/II, single arm, open-label and dose-escalation study designed to determine the safety profile and the recommended phase III dose of bosutinib when administered in combination with atezolizumab in naïve patients with chronic myeloid leukemia in chronic phase.

The investigator should document and explain any deviation from the approved protocol. All significant protocol deviations will be recorded and reported in the Clinical Study Report.

6.2. Analysis Populations

All data will be received from the sponsor duly anonymized. All analyzes carried out and results of software applications will be duly dated and stored.

Full Analysis Set: The full analysis set (FAS) comprises all patients who complete the first three phases of treatment (combination of bosutinib and atezolizumab) successfully.

Safety Set: The safety set (SS) includes all patients who received at least one dose of study medication. Reporting and analysis of safety information for these patients will be split into subsets by study phases.

Per-Protocol Set: The per-protocol set (PPS) consists of a subset of the patients in the FAS who are compliant with requirements of the clinical study protocol (CSP). A compliance of 70% with bosutinib treatment will be necessary to be included in the PPS. Protocol deviations leading to exclusion from the PPS will be detailed in the Clinical Study Report.

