4 DEFINITION OF TERMS

Assessment	A procedure used to generate data required by the study.
Accelerated Phase (AP)	
• $\geq 15\%$ blasts in the peripheral blood or bone marrow aspirate, but $< 30\%$ blasts in both the peripheral blood and bone marrow aspirate;• $\geq 30\%$ blasts plus promyelocytes in peripheral blood or bone marrow aspirate;• $\geq 20\%$ basophils in the peripheral blood;• Thrombocytopenia ($<100 \times 10^9/L$) that is unrelated to therapy.
Blast Crisis (BC)	$\geq 30\%$ blasts in peripheral blood or bone marrow aspirate Appearance of extra medullary involvement other than hepatosplenomegaly proven by biopsy (i.e., chloroma).
Complete Hematologic Response (CHR)	
• Complete normalization of peripheral blood counts with leukocyte count $<10 \times 10^9/L$• Platelet count $<450 \times 10^9/L$• No immature cells, such as myelocytes, promyelocytes, or blasts in peripheral blood• No signs and symptoms of disease with disappearance of palpable splenomegaly
Complete Molecular Response (CMR)	Undetectable BCR-ABL levels with high sample sensitivity (10^{-5} or greater) for a minimum of 2 years.
Cytogenetic Response (CyR)	
• Complete (CCyR): 0% Ph+ metaphases.• Partial (PCyR): > 0 to 35% Ph+ metaphases.• Minor (mCyR): >35 to 65% Ph+ metaphases.• Minimal: >65 to 95% Ph+ metaphases.• None: > 95 to 100% Ph+ metaphases.
Cycle of treatment	28 days of treatment
Disease Progression	The following events are considered disease progression: 
• AP.• BC.• CML-related death.
Enrollment	It is the time until all patients are included in the study, i.e. all patients received at least one dose of study medication. Previously they must have signed an informed consent (i.e., prior to starting any of the procedures described in the protocol).
Full Analysis Set (FAS)	The full analysis set (FAS) comprises all patients who complete the treatment with bosutinib in combination with atezolizumab for 12 cycles successfully.

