Medicinal product for Human Use or Investigational Drug	Any substance or combination of substances presented as having properties for treating or preventing disease in human beings or which may be used in or administered to human beings either with a view to restoring, correcting or modifying physiological functions by exerting a pharmacological, immunological or metabolic action, or to making a medical diagnosis (Royal Decree 1090/2015, of 4 December).
Loss of Complete Hematologic Response	Loss of CHR is defined as the appearance of any of the following, confirmed by a second determination ≥ 4 weeks later (unless associated with progression to AP/BC or CML-related death): 
• WBC count that rises to $> 20.0 \times 10^9/L$;• Platelet count that rises to $\geq 600 \times 10^9/L$;

	
• Progressing hepatosplenomegaly to a size \geq 5 cm below the left intercostal margin;• Appearance of \geq 5% myelocytes + metamyelocytes in the peripheral blood;• Appearance of blasts or promyelocytes in the peripheral blood.
Molecular Response (MR)	
• MMR – BCR-ABL \leq 0.1% (IS).• MR4 – BCR-ABL \leq 0.01% (IS).• MR4.5 \leq 0.0032% (IS).• UNDETECTABLE.
Overall Survival (OS)	OS is calculated from the first day of therapy to the date of death. Surviving patients will be censored at the time of the last follow-up.
Subject Number	A unique identifying number assigned to each patient who enrolls (i.e. signs the IC) in the study.
Per-Protocol Set (PPS)	A subset of the full analysis set (FAS) who is compliant with the clinical study protocol (i.e. Composed by subjects that have not incurred in major protocol deviations that could jeopardize the validity of the data and the study outcomes).
Premature Patient Withdrawal	When a subject exits from the study prior to the planned completion of all study treatment administration and/or assessments or procedures. From this time, all study treatment administration is discontinued and no further assessments or procedures will be done, other than the monitoring for progression and/or survival.

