11.6 Dose Modification and Dose Delay

The following section summarizes dosing modifications of bosutinib or atezolizumab to manage possible toxicity. Administration of bosutinib or atezolizumab could be stopped for an individual subject in the event of a treatment-related toxicity that, in the Investigator's assessment, warrants discontinuation. Exceptions to these guidelines will require approval from the Medical Monitor.

A maximum discontinuation of 1 month is allowed for the treatment with bosutinib if required due to the onset of adverse events, investigator decision, or other major circumstances. If a subject discontinued treatment for more than one month he/she will be withdrawn from the study and the appropriate follow-up procedures will be conducted. Also, to be included in the

efficacy analysis (Per protocol set population), a subject must comply with at least 70% of treatment with bosutinib. Regarding atezolizumab treatment, fail to administrate up to 3 out of the 11 administrations scheduled, will be allowed to continue in the study. If, for any reason, atezolizumab could not be administered 4 or more times during the course of the study, the subject will be withdrawn from the study and the appropriate follow-up procedures will be conducted. All deviations from the scheduled treatments regime shall be recorded in the patients' clinical history and the eCRF and explained if required.

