12 VISIT SCHEDULE AND ASSESSMENTS

12.1 Schedule of Events

Details on scheduling and sample collection are described in Tables 14-17. The tables 14 and 15 for 1st group of patients (first 10 patients included), and the tables 16 and 17 for 2nd group of patients (the last 26 patients included).

All data obtained from these assessments must be recorded in the source documentation. The CRF will not be used as a source document for any study data.

Please maintain a special awareness of the assessments of the primary and secondary endpoints.

All visits should be completed on the designated day or as close as possible. However, the windows allowed by protocol will be:

- For visits that take place every two weeks, the window will be ± 3 days.
- For visits that take place every 4 weeks, the window will be ± 3 days.
- For visits that take place every 3 cycles (every 12 weeks), and the End of Treatment visit, the window allowed will be ± 14 days.

For this purpose, a cycle equal to 28 days (4 weeks) will be defined and one month will be considered to be equivalent to one cycle.

Table 14. Schedule of Assessments 1st and 2nd Therapies for the First 10 Patients

The following visit schedule will apply if the atezolizumab dose does not need to be adjusted during 2nd therapy due to DLTs. If the dose of atezolizumab has to be modified to the 840 mg every two weeks, additional visits will be scheduled for the administration of atezolizumab. The only procedure to be conducted during these additional visits is the administration of atezolizumab

1 st Group of Patients (The 10 First Patients)		1 st Therapy		2 nd Therapy													
VISIT	Visit 0	Visit 1	Visit 2	Visit 3	Visit 4	Visit 5	Visit 6	Visit 7	Visit 8	Visit 9	Visit 10	Visit 11	Visit 12	Visit 13	Visit 14	Visit 15	Visit 16
Cycle	Screening / Baseline	Cycle 1		Cycle 2		Cycle 3		Cycle 4	Cycle 5	Cycle 6	Cycle 7	Cycle 8	Cycle 9	Cycle 10	Cycle 11	Cycle 12	Cycle 13
Day within Cycle (Visit Window ± 3 Days)	-28/-1	1	15	1	15	1	15	1	1	1	1	1	1	1	1	1	1
Consecutive Days in the Study (D)	-28/-1	D1	D15	D29	D43	D57	D71	D85	D113	D141	D169	D197	D225	D253	D281	D309	D337
Informed Consent	X																
Eligibility	X	X ⁽¹⁾															
Inclusion/Exclusion Criteria (Checklist)	X	X ⁽¹⁾															
Medical/Surgical History and Demographics	X																
Recent Medication Prior to First Dose of IMP	X	X ⁽¹⁾															
Leukemia Diagnosis and Prior Cancer Therapy	X																
Sokal Risk Score	X																

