6.4. Outcome definitions

The primary objective is to evaluate the safety profile of bosutinib 400 mg daily in combination with atezolizumab as first line treatments in participants with chronic myeloid leukemia. The safety set population will be used for all safety analyses. For a detailed description of safety variables analysis see the 6.9 Safety Data Analysis section.

➤ Secondary variables:

- Major Molecular Response (MMR) and Molecular Response (MR) rates at 3, 6, 12 months and at the End of Treatment (EoT) visit.
- Percentage of participants alive at months 6 and 12 and at the EoT visit.
- Number of confirmed MR4 and MR4.5 at end of treatment.
- The rate of confirmed MR4 and MR4.5 at the end of treatment.
- Number of Complete Cytogenetic Responses (CCyR) at 1 year]
- The rate of Complete Cytogenetic Response (CCyR) at 1 year.
- Number of days to response (CCyR, MMR, MR4, MR4.5). [Time Frame: at the EoT visit]
- The median time to response and the overall estimated probability of response (CCyR, MMR, MR4, MR4.5).
- Number of overall surviving patients [Time Frame: at the EoT visit]
- Number of progression-free survival patients.[Time Frame: at the EoT visit]
- Number of failure-free survival patients. [Time Frame at the EoT visit]
- Number of event-free survival patients. [Time Frame: at the EoT visit]
- Immunological Studies: phenotypic Assays:
 - Cell characterization: NK cells (CD3- CD56+; CD16+ CD56+; TNF α ; IFN α ; Granzyme b NK-LGL cells (CD56+ CD57+), T-LGL cells (CD3+ CD57+), CD8 TCR α/β , NK markers (NKG2D, KIR2DL2/DL3/DS2, KIR2DL5B).
 - b. Differentiation and maturation (NKG2A/CD16) and proliferation (NK67) markers of NK cells.

- c. CD4+ T cells activation markers: CD25 CD69 HLA-DR.
- d. Predictive markers of CML relapse: T regs (CD4+ CD25int-hi CD127low), CD8+ T cells (PD-1/PD-L1) and plasmacytoid dendritic cells (CD86+).

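### The full analysis set and the per-protocol set admit only combination completers, so survival at months 6 and 12 is fixed at 100% and response rates are likely to be overstated

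*SAP*

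**What the plan says.** SAP 6.2, repeated in Protocol 15.1.1, defines the main set by completion: "The full analysis set (FAS) comprises all patients who complete the first three phases of treatment (combination of bosutinib and atezolizumab) successfully". Protocol section 4 is more specific: "The full analysis set (FAS) comprises all patients who complete the treatment with bosutinib in combination with atezolizumab for 12 cycles successfully". Neither document says what counts as successful completion. The per-protocol set (PPS) is a subset of the FAS that also requires 70% bosutinib compliance.

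The sets are assigned to analyses as follows.

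- **Safety:** "The safety set population will be used for all safety analyses" (SAP 6.4; likewise Protocol 15.3.1). The safety set is everyone with at least one dose.
- **Baseline tables:** safety set and FAS (SAP 6.3, Protocol 15.2).
- **Secondary efficacy:** SAP 6.4 and 6.5 and Protocol 15.4.2 name no set. The only link is in Protocol 11.6, on inclusion in the "efficacy analysis (Per protocol set population), a subject must comply with at least 70% of treatment with bosutinib".

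The secondary endpoints include "Percentage of participants alive at months 6 and 12 and at the EoT visit", overall and progression-free survival, and MMR, MR4, MR4.5 and CCyR. The investigator may withdraw a patient "if he/she does not comply with the protocol, due to AEs or treatment inefficacy or toxicity" (SAP 5.3). After withdrawal, "no further assessments or procedures will be done, other than the monitoring for progression and/or survival" (Protocol section 4).

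**The concern.** Membership of the FAS and PPS depends on what happens during treatment. A patient who dies, or who is withdrawn for toxicity or lack of effect, before the combination ends belongs to neither set. Patients lost in the first monotherapy cycle are also excluded.

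Two things are at stake if efficacy is analysed as Protocol 11.6 indicates. First, percent alive at months 6 and 12 carries no information. Overall and progression-free survival, which the protocol starts at first dose, would contain about a year in which no death can be counted. Second, molecular and cytogenetic response rates would be computed after removing patients who are plausibly less likely to respond. The rationale in Protocol section 7 is that adding atezolizumab raises molecular response, and Protocol 6.2 supplies a bosutinib-alone figure of 47% MMR at one year. A completer rate well above 47% could look like a combination effect when selection alone produced it.

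**Working it through.** **The plan's own figure.** SAP 4.3 and Protocol 15.5 plan 36 patients and assume that at most 15% will not reach the combination: 36 × 0.85 = 30.6. This reproduces the stated 30-31.

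**Survival landmarks**

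- Time needed to enter the FAS (Protocol 11.5): 1 monotherapy cycle + 12 combination cycles = 13 × 28 = 364 days.
- Time scale (Protocol 12.1): "one month will be considered to be equivalent to one cycle". The survival clock starts on the first day of therapy (Protocol section 4).
- Month 6 = 1 + 6 × 28 = D169. Month 12 = 1 + 12 × 28 = D337. Both precede day 364.
- Every FAS or PPS member is therefore alive at both landmarks, and the estimate is n/n = 100% whatever happens in the trial. The exact 95% interval depends on n alone: 88.8-100% for n = 31, 86.3-100% for n = 25.
- In all 36 treated patients the estimate can move. One assumed death before month 12 gives 35/36 = 97.2% (85.5-99.9%); three give 33/36 = 91.7% (77.5-98.3%).

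Only death is excluded with certainty. Withdrawal at progression is not mandatory, so a completer could have progressed.

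**Response rates (illustration)**

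Take 17 responders at 12 months among 36 treated patients, 47.2%, which matches the bosutinib-alone 116/246 = 47.2% in Protocol 6.2. Suppose first that every responder completes. Losses during the combination are assumptions, because the documents give no figure. Intervals are exact (Clopper-Pearson).

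| Denominator | Derivation | Rate (95% CI) |
|---|---|---|
| All treated | 36 | 17/36 = 47.2% (30.4-64.5) |
| After 15% cycle-1 loss | 36 × 0.85 = 30.6, taken as 31 | 17/31 = 54.8% (36.0-72.7) |
| Further 10% loss | 30.6 × 0.9 = 27.5, taken as 28 | 17/28 = 60.7% (40.6-78.5) |
| Further 20% loss | 30.6 × 0.8 = 24.5, taken as 24 | 17/24 = 70.8% (48.9-87.4) |

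The last row is an upper bound. Of its 70.8 − 47.2 = 23.6 points, 54.8 − 47.2 = 7.6 come from patients who never receive atezolizumab. The other 70.8 − 54.8 = 16.0 come from losses during the combination.

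Now suppose instead that non-completers respond at half the completers' rate p, with 17 responders in total:

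- 31 completers: p = 17/(31 + 0.5 × 5) = 50.7%, an overstatement of 3.5 points.
- 24 completers: p = 17/(24 + 0.5 × 12) = 56.7%, an overstatement of 9.4 points.

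If completers and non-completers respond equally, p = 17/36 and there is no bias.

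**The case against.** The strongest reply is that the 100% result is conditional. No statistics section assigns survival or response to the FAS or PPS, and the one link is a parenthesis in a dose-modification section. Other text suggests a wider population: Protocol 12.14 has molecular response assessed in every patient, Protocol 12.20 collects survival and disease status at early termination, withdrawn patients stay under progression and survival monitoring, and the OS and PFS definitions carry no completer restriction. This is fair as to certainty. But those passages govern data collection and none assigns an analysis set. Either Protocol 11.6 governs and the survival result is predetermined, or no efficacy population is specified and it can be chosen after the data are seen. The SAP 6.7 sensitivity analysis uses complete data only and restores nobody.

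The time scale can also be questioned. In calendar months, month 12 falls at about 1 + 12 × 30.44 = D366, just after day 364. The month-equals-cycle rule in Protocol 12.1 points to D337, and month 6 is fixed under either convention. The phrase about three phases in SAP 6.2 is ambiguous, since Protocol 11.5 counts the final monotherapy as the third phase. Requiring all 25 cycles (day 700) would fix survival at end of treatment too, so that reading makes matters worse.

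On size, the protocol itself describes life expectancy in this disease as near normal, so the survival gap in points is small. The 71% is an extreme case; using 25 completers instead of 24 gives 17/25 = 68%. The 15% loss is the plan's stated maximum. These endpoints are descriptive and secondary in an exploratory study, and no decision rule uses them. All of that stands and limits the consequence, but it does not make a completer set suitable for these endpoints.

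**Conclusion.** The concern holds and should be corrected before analysis. In the only efficacy population the documents name, percent alive at months 6 and 12 can only be 100%, and the overall survival curve is flat to day 364. This rests on reading Protocol 11.6 as governing and on the protocol's 28-day month.

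Response rates are expected to be biased upward. In the illustration the overstatement is 3.5 to 9.4 points if non-completers respond half as often, at most about 24 points against all treated patients, and at most about 16 points against patients who received atezolizumab. It is zero if completion is unrelated to response, but withdrawal for inefficacy and toxicity makes that unlikely. The size depends on combination-phase losses that the documents do not give.

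The primary safety analysis and the DLT rules use other definitions and are not affected.

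**What to change.** 1. Redefine the FAS in SAP 6.2 and Protocol sections 4 and 15.1.1 as all patients with at least one dose of study drug.
2. Add a set of all patients with at least one atezolizumab dose, for response rates attributed to the combination.
3. State in SAP 6.4-6.5 which set each secondary endpoint uses, and align Protocol 11.6 and 15.4.2.
4. Report MMR, MR4, MR4.5 and CCyR at the fixed landmarks over everyone in the set, counting unassessed or withdrawn patients as non-responders. Other rules are possible; whichever is chosen must be reconciled with the carry-forward and carry-backward method in SAP 6.6.
5. Estimate percent alive, OS and PFS from first dose in all treated patients.
6. Keep the present FAS only as a supportive set, labelled as combination completers.

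The cost is mainly SAP and protocol wording, with no extra patients. There is one operational addition: progression and survival monitoring after withdrawal is foreseen, but the visit schedules in Protocol Tables 14-17 contain no such contacts, so brief status contacts must be added. Reported response rates will probably be lower than under the completer definition.
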